Title: *Morning bright light to improve sleep quality in Veterans*

Publications:

Data collection ongoing.

Relevance:

This protocol has recruited 91 participants over 18 months, 60 of which underwent MBLT for 4 weeks. The primary purpose of this protocol was to assess feasibility outcomes, including recruitment rate, retention rate, and adherence to the light therapy. Of the participants with TBI, 88% of subjects remained adherent to light therapy for the full 4 weeks. Overall, 91% of subjects said they liked using the lightbox. We additionally found that MBLT improves self-reported sleep, mood, and quality of life in our pilot cohort, however, this study lacks a placebo device for comparison.

Research Design and Methods:

Veterans within the VA Portland Healthcare System (VAPORHCS) and non-Veterans will be recruited for participation in this study. This study will consist of at least 4 visits over the span of ~5-6 mo.

Study Overview and Timeline.

	Visit 1	Visit 2	At Home	Visit 3	Visit 4 Follow up
Time point:	Day 0	Week 2	Week 2-6	Week 6	Week 10
Informed consent	X				
Subject given actiwatch		X		X	
Conduct pain assessment		X		X	X
Subject given lightbox or sham		X			
Questionnaires		X		X	X
Daily use of intervention for 1 hour			X		
Total time	~120 min	~120 min	28 hours	~120 min	~120 min

- *Informed consent and HIPAA authorization.* Written and verbal informed consent will be obtained before all other Visit 1 activities and may take place on an earlier date if DocuSign is able to be used to facilitate the consent conversation.
 - In cases where DocuSign is not feasible, consent conversations will take place in office space available at the VAPORHCS Sleep Disorders Clinic (building 100-6C), in related outpatient clinical space, or in Research Service space approved for human subjects use

(building 101, rooms 432A, 430, 404), or in subjects' homes. Alternatively, consent may take place remotely via phone or video conferencing via mailed documents.

- Where DocuSign is feasible, study staff will initiate email of a DocuSign envelope providing subjects access to the consent and authorization forms ahead of the consent discussion. Subjects will then be guided through downloading the fully executed consent form.

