- Participants will be asked to fill out demographics information which will include their name (including name at birth), date of birth, city/town of birth, email and physical address, phone number, health history, and military history.
- Individuals without a medical record at the VA will be asked permission for study staff to request their medical record pertaining to sleep and traumatic brain injury.

Visit 2

- Visit 2 will occur ~2 weeks after visit 1. It can take place within the VAPORHCS Sleep Disorders Clinic (building 100-6C), in Research Service (building 101, rooms 432A, 430, 404, and 533), remotely via phone/video conferencing, or at the subject's home.
- *Questionnaires.* Subjects will complete baseline questionnaires. They take ~30 min to complete and include past medical history and self-reported measures on sleep, social habits, quality of life, mental health, pain, and other metrics related to subject's prior trauma exposure history. All questionnaires are validated and will be completed via pen and paper. Medical history and testing related to sleep will be accessed from the participants' VA medical records by study staff with VA credentials. Subjects may elect to complete these questionnaires at either this or subsequent visits as needed. Questionnaires may be mailed if completed remotely.
- *Equipment.* Subjects will be randomized to receive a lightbox (LightPad mini, Aurora Light Solutions) or sham-control modified negative ion generator. Devices will be modified by completely disconnecting the electrical wiring required for negative ion generation. This will be verified using a voltmeter. A small fan may be installed to emit a low humming noise as an indicator of activity. They will be instructed to use either device for 60 min every morning after waking up starting 2 weeks following this visit and continuing for 4 weeks. Light sensitive devices, called HOBOs, will be attached to the lightboxes which will track when the lightbox is turned on or off, as a secondary measure of light delivery.

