- *Actigraphy.* Subjects will be asked to wear an individually configured actigraphy watch (Phillips Respiration Actiwatch 2) for the entirety of the study. This actiwatch collects data related to subject's sleep-wake cycle, including activity (via a built-in accelerometer) and light exposure (via a built-in luxometer). Watches are user friendly, requiring no user input to operate, and batteries last for ~6 weeks. Subjects will be reminded to keep clothing from covering up the luxometer on the actiwatch as much as possible.
- *Study diary.* Subjects will be asked to fill out a study diary, with daily entries for the entirety of the study. They will record when they went to bed, when they woke up, when they used the lightbox, and days they went to work. At this point subjects will be educated on principles of good sleep hygiene, such that all subjects start at the same baseline with respect to their understanding of good sleep hygiene principles. Study diaries will be coded via subject's ID with no other identifiable information listed.
- *Pain testing.* Pressure-pain threshold and tolerance will be quantified using a pressure algometer (AlgoMed Computerized Pain Pressure Algometer), a validated device used both experimentally and clinically with the pressure stimulus delivered to the thumbnail/thenar region of the non-dominant hand. Threshold will be determined by the amount of pressure that the subject perceives as mildly painful. Tolerance will be determined by the amount of pressure that causes the subject to withdraw their hand. This test takes ~20 min to complete.
- *Pain testing.* Cold Pressor Test. The cold pressor test may be used at VAPORHCS and at visits that are conducted remotely. This test will consist of an ice bath that subject's are instructed to submerge

their non-dominant hand into. Threshold and Tolerance will be measured with a stop watch. Threshold will be determined by the amount of time that the subject perceives the temperature as mildly painful. Tolerance will be determined by the amount of time that causes the subject to withdraw their hand. This will be done during a single trial. The upper limit of allowing the hand in the icebath is 5 minutes.

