- *Pain testing.* Ischemic Pain Test. Ischemic pain testing may be used at VAPORHCS and at visits that are conducted remotely. This test will consist of a manual blood pressure cuff that is placed on the subject's non-dominant upper arm and inflated to 300 mmHg. Threshold will be determined by the amount of time that the subject perceives the constriction as mildly painful. Tolerance will be determined by the amount of time that the subject allows the constriction to continue. This will be done during a single trial. The upper limit of allowing the hand the constriction is 5 minutes.
- *Department of Defense Head Trauma Events Checklist (DoD HTEC).* Determination of TBI status occur through a semi-structured diagnostic interview following the DoD HTEC guidelines. This interview will take ~15 min to complete.
- *Reimbursement.* Subjects will be compensated with up to \$20

Visit 3

- Visit 3 will occur ~4 weeks after Visit 2 and will take place within the VAPORHCS Sleep Disorders Clinic (building 100-6C), in Research Service (building 101, rooms 432A, 430, 404, and 533), remotely via phone/video conferencing, or at the subject's home.
- *Measures.* The same series of questionnaires and pain testing conducted at Visit 1 will be repeated.
- *Equipment.* Subjects will return all equipment, including the actiwatch, lightbox and/or sham device.
- *Reimbursement.* Subjects will be compensated with up to \$60

Visit 4

- Visit 4 will occur ~4 weeks after Visit 3 and will take place within the VAPORHCS Sleep Disorders Clinic (building 100-6C), in Research Service (building 101, rooms 432A, 430, 404, and 533), remotely via phone/video conferencing, or at the subject's home.
- *Measures.* The same series of questionnaires and pain testing conducted at Visit 1 will be repeated.
- *Reimbursement.* Subjects will be compensated with up to \$20
- *End of study debrief.* Subjects will be debriefed about our experimental design, given the inclusion of a placebo-controlled condition. We will provide subjects with a written description that we will describe to them in person and address any questions they may have.

Mailed forms and equipment. In an effort to reduce subject's time at the Portland VA we may mail consent forms, questionnaires, equipment and pre-addressed, pre-paid return envelopes directly to their homes. Instructions will be provided via phone or video conferencing.

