Video Conferencing. If the subject is comfortable and equipped, we may conduct visits using video conferencing, such as VA Video Connect or other VA approved methods (skype, facetime, google hangouts, etc.). A link to the video chat will be emailed participants via Azure RMS encrypted email. For VA Video Connect (VVC), this email is entered into the VCC platform and an email is automatically generated.

At home visits. In special circumstances study personnel may travel to the subject's homes in order to conduct the visit more comfortably. Equipment, data, and specimens will travel in between the home and the VA only.

Phone calls. In between visits subjects will be contacted up to 2 times per week as needed. They will be assessed for understanding and compliance and given the opportunity to asked questions. Questions will be asked about their sleep, pain, and quality of life metrics.

Emails. Communication via RMS Azure encrypted email may be established between the subject and study coordinator in order to allow subjects to freely ask any questions they may have.

Study Population:

Number of subjects. The target population will consist of n=100 subjects. In order to meet this enrollment target we anticipate that up to 400 individuals may need to be recruited (consented) and screened.

Eligibility Criteria. Only Veterans and non-Veterans who are physically and mentally able to provide written and verbal informed consent and have a medical record-confirmed or physician confirmed diagnosis of TBI, will be included in this study. Additional criteria are as follows:

- 1) Current self-reported sleep-wake disturbances (defined by clinically abnormal Insomnia Severity Index and/or Functional Outcomes of Sleep scores)
- 2) Moderate to severe pain (defined as a score of ≥ 4 on an 11-point scale⁹⁰) persisting for longer than 6 months
- 3) Do not have a diagnosis for dementia
- 4) Are not currently using a lightbox or negative ion generator
- 5) Are not night-shift workers
- 6) Are English speaking with phone access
- 7) Are 18 years of age or older
- 8) Do not have macular degeneration or bipolar disorder (both are relative contraindications to regular bright light exposure)
- 9) No suicidal ideation
- 10) No cancer diagnosis in the past 6 months
- 11) At least 6-12 months of being surgery free
- 12) No evidence of drug and alcohol dependency (defined by the substance abuse and dependency scale).
- 13) Are currently living within the United States.

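### The 300 mmHg manual-cuff pain test is permitted at remote visits, which may be by phone alone, where staff can neither see the gauge nor confirm that the cuff is released

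*Protocol*

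**What the plan says.** Under Visit 2, the Ischemic Pain Test paragraph says that "Ischemic pain testing may be used at VAPORHCS and at visits that are conducted remotely". The device is a "manual blood pressure cuff that is placed on the subject's non-dominant upper arm and inflated to 300 mmHg". The time limit reads: "The upper limit of allowing the hand the constriction is 5 minutes". Threshold and tolerance are recorded as times, and the participant decides when tolerance has been reached.

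The Study Overview and Timeline table marks "Conduct pain assessment" at Visits 2, 3 and 4. The location line for each of these visits includes "remotely via phone/video conferencing, or at the subject's home", so a remote contact and a visit at home are separate options. On video the protocol says "If the subject is comfortable and equipped, we may conduct visits using video conferencing". On staff travel it says "In special circumstances study personnel may travel to the subject's homes in order to conduct the visit more comfortably". Eligibility criterion 6 asks for phone access and does not mention video. Criterion 13 asks only for US residence.

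The Risks and Side Effects section says that the cuff will be deflated at once if the participant reports discomfort beyond mild or wants to stop. It does not say who deflates it, and it gives no separate wording for remote visits.

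**The concern.** A manual cuff at 300 mmHg for up to 5 minutes is a procedure in which the person responsible should be able to see the pressure, keep the time and be sure that the cuff comes down. In the clinic, or with staff in the home, all three are straightforward. On live video they can be done if the arm and gauge are on screen. On a phone call staff can time the test and tell the participant to stop, but for everything else they depend on what the participant says.

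What is at stake is participant safety, at a modest level. There is a secondary data point: threshold and tolerance are times under a nominal 300 mmHg stimulus, and by phone that stimulus is unverified.

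**Working it through.** No arithmetic applies. The question is whether the written permission reaches an audio-only visit and, if so, whether the stated safeguards still work there.

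**Step 1. Does the permission reach a phone-only visit?**
- The Ischemic Pain Test paragraph allows the test at remote visits and sets no condition on the type of remote visit.
- The location lines for Visits 2, 3 and 4 give phone and video together as the remote mode and list the home separately. Remote therefore does not mean that staff are in the home.
- The Video Conferencing paragraph makes video conditional and optional.
- Criterion 6 lets in a participant who has only a phone.
- The At home visits paragraph keeps staff travel for special circumstances, so it is not the routine substitute when video is unavailable.
- The paragraph on mailed forms and equipment says that instructions will be given by phone or by video.

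No sentence in the protocol excludes a phone-only cuff test, so the permission does reach one.

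**Step 2. Do the safeguards carry over to a phone call?**
- *Pressure of 300 mmHg.* Staff cannot see the gauge. They can ask the participant to read it out.
- *Five-minute cap.* Staff can keep time and call the stop. They cannot see whether the cuff comes down when it is called.
- *Immediate deflation.* Staff can ask for it. They cannot do it, and they have only the participant's report that it was done.

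With staff present, or on video with arm and gauge in view, each of these can be observed.

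**Step 3. Is the cold pressor test in the same position?** The protocol says that "The cold pressor test may be used at VAPORHCS and at visits that are conducted remotely", so the permission is identical, but the safeguards differ. In the risk section the discomfort stop for the ice bath is a spoken instruction to take the hand out, which works by phone. Only compliance with its 5-minute limit would go unobserved, and staff can still call that limit.

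**Step 4. What would restricting both tests remove?** The cold pressor and ischemic tests are the two pain tests with an express permission for remote visits. The pressure algometer paragraph has none. Barring both from phone visits could leave a participant without video with no expressly permitted quantitative pain test at that visit. The cuff and the ice bath should therefore be treated differently.

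**The case against.** The strongest case against the point has four parts.

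*The hazard is inferred.* The test is discretionary, the location line is general and also covers questionnaires and interviews, and nothing directs a cuff test by audio alone. The step-by-step guidance speaks of participants returning to the facility for Visits 2 to 4. This stands as a limit on how often the situation would arise, and the frequency may be nil. It does not change what the permission allows.

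*The operating detail may be elsewhere.* The appendix lists an information sheet and phone scripts that are not shown, and these may say who holds the bulb and how to release the valve. So it cannot be said that no such instruction exists. The point rests only on the protocol's own permission, which sets no limit on visit mode.

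*The participant controls the test.* Tolerance ends when the participant chooses, and someone in pain has every reason to release the cuff. Spoken confirmation has some value. Both arguments reduce the risk. Neither lets staff confirm pressure or release, and the protocol does not say that release is taught before inflation.

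*The stated harm is slight.* The risk section describes mild discomfort and temporary numbness or sensitivity. That is accepted, and no greater harm is claimed here.

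A reader might also infer that the cold pressor test should be barred from phone visits. The document does not support this, because its spoken stop works on a call and removing it could leave no remote pain test for some participants.

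**Conclusion.** The point holds as a modest participant-safety matter. As written, the protocol permits a manual cuff at 300 mmHg for up to 5 minutes on a call where staff can see neither arm nor gauge. Its assurance of immediate deflation is then something staff can ask for but not carry out or confirm.

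The size cannot be put as a number. The protocol does not say how many visits will be by phone alone or how many of those would include the cuff. The effect on inference is small, because the cuff test is optional and the Aim 2 hypothesis names self-reported pain and pressure algometry.

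A reader might go further and conclude that the protocol directs unsupervised cuff inflation at home, or that participants face serious injury. The text supports neither: the first is permitted by omission and not instructed, and the stated effects are mild and temporary.

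The conclusion assumes that a phone visit has no one from the study in the room, which follows from the separate listing of remote and home visits. It also assumes that the documents not shown do not restrict the visit mode. If they do, that restriction should be brought into the protocol.

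**What to change.** In the Ischemic Pain Test paragraph, allow the cuff test only (a) with study staff physically present, in the clinic or at a home visit, or (b) on live video with the arm and gauge in view. State that the participant is shown how to release the cuff before inflation, and that staff keep time and call the 5-minute stop.

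In Risks and Side Effects, reword the ischemic entry so that at video visits the participant releases the cuff on instruction and staff confirm on screen that it is down.

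Leave the cold pressor test available at phone visits, with staff calling its 5-minute stop, so that participants without video still have a quantitative pain test.

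The change is to protocol wording and uses visit modes that already exist. Its cost is that a participant without video who cannot have a staffed visit misses the optional cuff test at that visit. Because US residence is the only geographic requirement and home visits are kept for special circumstances, this will fall mainly on distant participants.

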Morning Bright Light Therapy: Precedent and Protocol. In a recent systematic review and meta-analysis of the effects of light therapy on sleep problems that included 53 studies, the largest effect sizes (Hedge's *g* range: 0.38 to 1.13) were found on insomnia symptoms and circadian outcomes.³¹ Within these categories, subjective sleep complaints were also found to have larger effect sizes compared to objective sleep-time variables. For example, studies employing bright light therapy to improve insomnia showed Hedge's *g* effect sizes of 1.13 for complaints of fatigue, 0.80 for insomnia symptoms, 0.77 for sleep quality, and 0.44 for daytime sleepiness. Within this same group of studies, objective sleep-time variables showed Hedge's *g* effect sizes of 0.45 for sleep onset latency, 0.44 for total sleep time, 0.47 for wake after sleep onset, and 0.38 for sleep efficiency. Similar effect sizes and pattern between subjective and objective sleep metrics were also reported for studies using bright light therapy to address circadian rhythm sleep disorders. Accordingly, the majority of the expected effect sizes for outcomes we propose in the present application have been shown to be moderate to large, albeit in a non-TBI civilian population.

The key moderator of the response to morning bright light therapy was found to be the administered light intensity (i.e., lux), although treatment duration was also relevant. In the aforementioned studies employing bright light therapy to treat insomnia the mean light intensity was 4,800 lux and corresponded to an overall effect size of 0.47. The moderator effect of light intensity was 0.08, meaning the estimated effect size for a light intensity of 10,000 lux increases to ~0.85. Additional relevant, albeit non-significant, moderators were noted to be treatment duration and treatment instructions. Previous work has also established that treatment intensity and duration are key moderators for the effectiveness for bright light therapy,⁷⁷ which should not be surprising given the neuroanatomical connection underlying these processes being dependent on total photopic flux (i.e., photopic input activating intrinsically photosensitive retinal ganglion cells). Finally, although non-significant, instructions for carrying out the light therapy protocol also appeared important. We have also found clear instruction to be critical toward effective implementation and have developed several strategies to improve communication.

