The goals of our data management system are to maintain data accuracy and security, and to ensure efficient access for monitoring and analysis. All study personnel doing data collection will be carefully trained in their tasks (i.e., collection methods, security, auditing and tracking, prevention and detection of intrusion, back-up and recovery, quality control, monitoring and reporting.

Step-by-Step Guidance on Conducting the Study

Recruit subjects from methods described in “Subject Identification/Recruitment” section

1. Complete Visit 1.
 - a. Obtain written and verbal informed consent and HIPAA authorization from subjects
2. Schedule time to return to the VAPORHCS for Visit 2.
3. Complete Visit 2.
 - a. Provide subjects with lightbox or disabled negative ion generator
 - b. Collect subjects initial questionnaire data, complete pain testing, provide study diary
 - c. Compensate subjects with up to \$20
4. Schedule time to return to the VAPORHCS for Visit 3.
5. Complete Visit 3.
 - a. Collect subjects post-study questionnaire packet and complete pain assessment.
 - b. Collect subjects actiwatch, lightbox or negative ion generator, and study diary
 - c. Compensate subjects with up to \$60
6. Schedule time to return to the VAPORHCS for Visit 4.
 - a. Collect subjects follow-up questionnaire packet and complete pain assessment.
 - b. Compensate subjects with up to \$20
7. Thank subjects for their participation.

References & Literature Cited:

1. Centers for Disease and Control. Injury Prevention and Control: Traumatic Brain Injury and Concussion [Internet]. 2016. Available from: http://www.cdc.gov/traumaticbraininjury/get_the_facts.html
3. Okie S. Traumatic brain injury in the war zone. *N Engl J Med* 2005;352:2043–7.
4. Ouellet M-C, Savard J, Morin CM. Insomnia following Traumatic Brain Injury: A Review. *Neurorehabil Neural Repair* 2004;18(4):187–98.

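### Between-visit calls are left to the discretion of staff not stated to be blinded, so attention can differ between arms and nothing equalises or records it

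*Protocol*

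**What the plan says.** All references are to the Protocol.

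- **Frequency** (Research Design and Methods, Phone calls): "In between visits subjects will be contacted up to 2 times per week as needed".
- **Content** (same paragraph): "They will be assessed for understanding and compliance and given the opportunity to asked questions", followed by "Questions will be asked about their sleep, pain, and quality of life metrics".
- **E-mail** (Emails): an encrypted channel to the study coordinator may be opened "in order to allow subjects to freely ask any questions they may have". No limit or log is given.
- **Arms** (Visit 2, Equipment): "Subjects will be randomized to receive a lightbox (LightPad mini, Aurora Light Solutions) or sham-control modified negative ion generator".
- **Device handling** (Step-by-Step Guidance on Conducting the Study): at Visit 2 the team is to "Provide subjects with lightbox or disabled negative ion generator", and at Visit 3 to "Collect subjects actiwatch, lightbox or negative ion generator, and study diary".
- **The team's view of instruction** (Morning Bright Light Therapy: Precedent and Protocol): "We have also found clear instruction to be critical toward effective implementation and have developed several strategies to improve communication". The same section describes treatment instructions as a non-significant moderator in the cited meta-analysis.

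The Protocol does not say who makes the calls, whether those staff are blinded, or that contact must be equal across arms or recorded.

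**The concern.** A sham arm is meant to absorb everything except the light, including the attention that comes with taking part. That works only if attention is delivered alike in both arms. Here its amount is decided person by person after randomisation, by staff who can be expected to know the device. Randomisation gives no protection against a difference that arises after allocation.

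The calls are also more than administrative. They support use of the device and go over the same domains that Aims 1 to 3 measure, each of which includes a self-reported outcome. If one arm were called more often, part of a difference in those outcomes could come from the calls. Without a record of contacts, nobody could later tell whether this had happened.

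**Working it through.** No figure in the Protocol can be reproduced for this point, because it concerns conduct. The check has three parts.

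**1. What the rule allows.** The input is a maximum of 2 calls per week with no minimum (Phone calls).

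- 4 weeks of device use: 2 × 4 = 8, so 0 to 8 calls per participant.
- Visit 2 (Week 2) to Visit 4 (Week 10): 2 × 8 = 16, so 0 to 16. This includes the 4 weeks after the device is returned at Visit 3, when there is no device use to support, so the 8 is the relevant figure.

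These are limits for one participant. A gap of 8 between arm means would need everyone in one arm to be called twice a week and no one in the other to be called at all. One extra call per week in one arm would be a gap of 1 × 4 = 4. Both follow the rule as written.

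The contact window is itself unclear. The Visit 2 text starts device use two weeks after that visit and continues it for four weeks, which is 2 + 4 = 6 weeks. The timeline table and the Visit 3 text put Visit 3 four weeks after Visit 2. These passages must be reconciled. The interval between the visits would hold up to 2 × 4 = 8 or 2 × 6 = 12 calls.

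**2. Whether callers can be expected to know the arm.** This is an inference from three facts. A lightbox and an ion generator are different kinds of object. Study staff issue and collect them. A call about compliance has to refer to the device. Equipment may be mailed, so the handover is not always in person, but the third fact still applies. The exact statement is that callers are not stated to be blinded.

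**3. What a contact bias would do, by assumption only.** The documents give no effect per call, so the bias cannot be computed. For illustration, take 50 per arm (Power analysis), an assumed two-sided 5% level (the Protocol gives no number), no true light effect, and a bias of b standard deviations from unequal contact.

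SE = √(2/50) = 0.20

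P(reject) = Φ(b/SE − 1.96) + Φ(−b/SE − 1.96)

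| Assumed b (SD) | False-positive rate |
|---|---|
| 0 | 5.0% |
| 0.05 | 5.7% |
| 0.1 | 7.9% |
| 0.2 | 17.0% |
| 0.3 | 32.3% |

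The rates are the same for a bias in either direction. The first row is what equal contact would give. None of the non-zero values of b comes from the documents. The Power analysis postulates a sham response of half the MBLT effect, but that allows for response to the sham and not for contact that differs between arms.

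**The case against.** The best defence is that contact as needed is ordinary in a home-based trial, that the ceiling is the same for everyone, and that no imbalance has been shown. The last two statements are true, but a common ceiling does not equalise what happens beneath it.

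Several stronger readings are tempting, and the documents do not support them:

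- **That light users will need more calls, so the bias favours light.** Risks and Side Effects lists glare, headache and dryness for the lightbox, invites participants to call the coordinator, and expects no effects from negative ions in the other arm. But it calls the light effects minimal and uncommon, and nothing describes setup problems. Sham users who notice nothing might equally want more contact.
- **That the Protocol itself says coaching changes the treatment effect.** The instruction finding is labelled non-significant, and the team's own remark concerns implementation. Coaching that makes people use the light more would act through the light, which is different from an attention effect.
- **That lightbox use tracking will prompt extra calls.** The trackers are described for lightboxes only, but they do not transmit and must be docked to be read.

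Two further points stand in part. Aims 1 and 2 also have actigraphy and algometry, so the exposure is greatest for the self-reported measures. Phone scripts appear in the Appendix and are not shown. The text ties scripts to screening and e-consent, and a script for follow-up calls may exist, but a script alone would not fix the number of calls. An analysis plan could examine contacts only if they are recorded.

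**Conclusion.** The point holds as a weakness in the stated rule and not as a demonstrated bias. Followed exactly, the Protocol lets staff-initiated contact range from 0 to 8 calls per participant during the 4 weeks of device use. It lets that amount differ by arm, and it leaves no record. A between-arm difference in self-reported sleep, pain or quality of life could then partly reflect contact. Direction and size are unknown.

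The conclusion rests on two assumptions: that callers know the device, which is a well-supported inference, and that attention can shift self-reported outcomes. This is a cheap improvement worth making. It does not show that the design fails.

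**What to change.** Under Phone calls, replace the discretionary rule with one fixed schedule of staff-initiated calls, identical in both arms and within the existing maximum. Use one device-neutral script with the same questions for everyone. Moving the sleep, pain and quality-of-life questions out of the calls is optional, as long as both arms are asked the same.

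Keep participant-initiated calls and e-mails open. They cannot be equalised, so log every contact with its date, duration and who initiated it, and report contacts by arm.

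The cost is a wording change, a follow-up script and a simple contact log. Some participants will receive calls they would not have needed, within the limit already planned.
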